8.6.1 Assessments of bleeding episodes and treatment response

The severity of bleeding episodes is defined as

- Mild/moderate: Bleeding episodes that are uncomplicated joint bleeding episodes, muscular bleeding episodes without compartment syndrome, mucosal- or subcutaneous bleeding episodes. These bleeding episodes can be treated at home after visit 20 and details of the bleeding episodes should be entered in the eDiary by the patient's parent(s)/LAR(s).
- Severe: All intracranial, retroperitoneal, iliopsoas and neck bleeding episodes must be categorised as severe. Muscle bleeding episodes with compartment syndrome and/or bleeding episodes associated with a significant decrease in the haemoglobin level (>3g/dl) should also be reported as severe (it is the investigators decision if haemoglobin measurements should be performed). The investigator must be contacted if a severe bleeding episode occurs.

In case of treatment requiring bleeding episode occurs outside the trial site's opening hours and prior to home treatment or treatment outside trial site (Section [5.3.5](#)) has been initiated, the patient must be treated according to local procedure.

Bleeding Episode - information to be collected

Information about bleeding episodes prior to the 20 ED (V20) should always be recorded in eCRF. In case the patient is treated outside the trial site the trial site should be informed in case of a bleeding episode and the details hereof. After 20 EDs bleeding episodes must be recorded either in the eDiary (if treated at home) or in the eCRF (if treated at the trial site), see Section [12.3](#).

Protocol
Trial ID: NN7999-3895
UTN: U1111-1135-9557
EudraCT No.: 2012-004867-38

~~CONFIDENTIAL~~

| | | |
|----------|------------------|---------------------|
| Date: | 05 November 2019 | Novo Nordisk |
| Version: | 8.0 | |
| Status: | Final | |
| Page: | 65 of 119 | |

Classification and recording of severe bleeding episodes is the responsibility of the investigator and should always be registered in the eCRF.

- Date and time the bleeding episode started
- Date and time the bleeding episode stopped
- Cause of the bleeding episode
 - i.e. spontaneous, traumatic or due to surgery
- Anatomical location of bleeding episodes
- Treatment of bleeding episodes
 - amount, date and time of each dose of N9-GP
- Severity of treatment requiring bleeding
 - mild/moderate, severe
- Haemostatic response assessed by the 4-point scale defined in the below [Table 8-3](#)

Protocol
 Trial ID: NN7999-3895
 UTN: U1111-1135-9557
 EudraCT No.: 2012-004867-38

~~CONFIDENTIAL~~

Date: 05 November 2019
 Version: 8.0
 Status: Final
 Page: 66 of 119

Novo Nordisk

Table 8-3 4-point scale

| Classification | N9-GP dosing | Description |
|----------------|---|--|
| Excellent | 
 One dose within 8 hours | Abrupt pain relief and/or clear improvement in objective signs of bleeding |
| Good | 
 One dose within 8 hours | Noticeable pain relief and/or improvement in signs of bleeding |
| Moderate | 
 More than one dose within 8 hours | Probable or slight beneficial effect after the first injection |
| Poor | 
 More than one dose within 8 hours | No improvement or worsening of symptoms |

Re-bleed

Classification of re-bleed will be performed at the time of the statistical analysis, according to the following criteria:

A re-bleed is defined as a new bleeding episode within 72 hours after stopping of a previous bleeding episode at the same or a subset of the same anatomical locations

If a bleeding episode occurs in the same location later than 72 hours after stopping the treatment it is considered as a new bleeding episode

8.7 Surgery

Before any surgery is performed blood samples for assessment of FIX inhibitors must be taken and send to central lab unless samples has already been sent to central lab within the last 30 days. The results do not have to be available before the surgery.

Emergency surgeries are allowed in this trial if adequate supply of N9-GP is available at site to ensure haemostasis and wound healing.

Patients undergoing surgery will continue the regular visit schedule, but additional visits may be performed in the peri-operative period as decided by the investigator. Surgery will be documented as unscheduled visits. It is up to the investigator to decide how long the post-surgery period should be and when the patient should resume regular prophylaxis or pre-prophylaxis treatment. All N9-GP doses administered in relation to a surgery must be registered on the surgery form in the eCRF or eDiary.

Protocol
 Trial ID: NN7999-3895
 UTN: U1111-1135-9557
 EudraCT No.: 2012-004867-38

~~CONFIDENTIAL~~

| | | |
|----------|------------------|---------------------|
| Date: | 05 November 2019 | Novo Nordisk |
| Version: | 8.0 | |
| Status: | Final | |
| Page: | 67 of 119 | |

8.7.1 Minor surgery

Preventive N9-GP treatment before minor surgery including placement or removal of central venous access port can be performed within this trial at the investigator's discretion according to local guidelines. A dose of 40 IU/kg N9-GP prior to minor surgery is recommended to prevent perioperative bleeding episodes, see [Table 5-1](#). Definition of minor surgery, see Section [5.3.8](#). For minor surgery the following should be recorded in the eCRF:

- Date, time and volume of preventive dose before surgery
- Type of surgery
- Indication for surgery
- Location of surgery
- Date of surgery
- Start and stop date and time of surgery

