5.3.8 Surgery

Minor surgery

Minor surgeries (procedures where only one dose of N9-GP is considered sufficient prior to the surgery) can be performed while participating in this trial by administering a dose of 40 IU/kg N9-GP, see [Table 5-1](#).

Definition of minor surgery

Minor surgery is defined as an invasive operative procedure where only the skin, the mucous membranes or superficial connective tissue is manipulated. For this trial, examples of minor surgery include:

- Implanting and removing ports in subcutaneous tissue (see * in [Table 5-1](#))
- Skin excisions
- Drainage of abscess
- Simple dental procedures

Protocol
 Trial ID: NN7999-3895
 UTN: U1111-1135-9557
 EudraCT No.: 2012-004867-38

~~CONFIDENTIAL~~

| | | |
|----------|------------------|---------------------|
| Date: | 05 November 2019 | Novo Nordisk |
| Version: | 8.0 | |
| Status: | Final | |
| Page: | 28 of 119 | |

- Circumcision

Major surgery

Major surgery may be performed after 20 EDs in the current trial.

In a separate completed N9-GP surgery trial (NN7999-3773/paradigm™3) 13 adults and adolescent patients underwent major surgery where the haemostatic effect in all study participants was reported as either good or excellent and the N9-GP appeared to have a safe and well tolerated profile.

Major surgery in the current trial should be planned and conducted in accordance with the recommendations in the WFH Guidelines for the management of haemophilia.⁸ Determination of dose and dose intervals to achieve adequate haemostasis should include close monitoring of FIX activity trough and peak levels, taken into consideration the half-life of N9-GP and ongoing clinical evaluation of the haemostatic effect.

Major surgery may be performed using general anaesthesia, spinal anaesthesia, epidural anaesthesia, conscious sedation, local anaesthesia or with a combination of these modalities. The used sedative products should be listed in the concomitant medication.

Further details and requirements when performing major surgery are provided in Section [8.7](#).

Definition of major surgery

Major surgery is defined as any invasive operative procedure that require several days of FIX substitution therapy and/or where any one or more of the following occur:

- A body cavity is entered
- A mesenchymal barrier (eg pleura, peritoneum or dura mater) is crossed
- A fascial plane is opened
- An organ is removed
- When normal anatomy is operatively altered
- Major elective orthopaedic surgery

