Treatment with N9-GP during surgery will be included in the overall count of N9-GP EDs. Upon completion of the surgical/invasive procedure the patient will continue prophylactic treatment with N9-GP as before the surgery.

Protocol
 Trial ID: NN7999-3895
 UTN: U1111-1135-9557
 EudraCT No.: 2012-004867-38

~~CONFIDENTIAL~~

Date: 05 November 2019
 Version: 8.0
 Status: Final
 Page: 29 of 119

Novo Nordisk

Table 5-1 Intravenous N9-GP treatment

| Indication | Dosage* | Frequency |
|---|---|--|
| Pre-prophylaxis during main phase (prior to 20EDs) (pt. less than 24 months of age) | 40 IU/kg | On-demand or intervals longer than once weekly |
| Prophylaxis during main phase | 40 IU/kg | Once weekly (± 1 day) |
| Prophylaxis during extension phase | 40 IU/kg | Once weekly (± 1 day) |
| Mild/moderate bleeding episode | 40 IU/kg | Single dose for bleeding episodes. Additional doses only after consultation with the investigator |
| Severe bleeding episode (The investigator must be contacted) | 80 IU/kg, not exceeding 200 IU/kg per 24 hours | Single dose for bleeding episodes. Severe bleeding episodes can be treated with further dose if instructed by the investigator |
| Minor surgery | 40 IU/kg (*Port implantation: 80 IU/kg) | Single dose prior to surgery |
| Major surgery, only allowed after 20 EDs | In accordance with the WFH Guidelines ⁸ and local standard of practise | In accordance with the WFH Guidelines ⁸ and local standard of practise |
| Low titre inhibitor | 40 IU/kg | Once weekly (± 1 day) |

*The dose to administer will be calculated by IWRS and defined in whole mL for doses above 3mL.

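### Port placement has two stated doses, 40 IU/kg in Section 8.7.1 and 80 IU/kg in Table 5-1, and a shared asterisk leaves port removal unclear

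*Protocol*

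**What the plan says.** Three places in the protocol bear on the dose before a port procedure.

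- **Section 8.7.1 (Minor surgery)** opens with "Preventive N9-GP treatment before minor surgery including placement or removal of central venous access port" and leaves such treatment "at the investigator's discretion according to local guidelines". The next sentence is "A dose of 40 IU/kg N9-GP prior to minor surgery is recommended". It ends with a reference to Table 5-1. The section contains no separate figure for ports.
- **Section 5.3.8 (Surgery)** gives 40 IU/kg for minor surgery and also refers to Table 5-1. The first entry in its list of examples is "Implanting and removing ports in subcutaneous tissue", followed by a pointer to the asterisk in Table 5-1.
- **Table 5-1** has the column headers "Indication | Dosage* | Frequency". The dosage cell for minor surgery reads "40 IU/kg (*Port implantation: 80 IU/kg". The only footnote marked with an asterisk says: "The dose to administer will be calculated by IWRS and defined in whole mL for doses above 3mL".

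Two other sections touch on the point. Section 8.5 says that N9-GP is given in line with Table 5-1. Section 8.1.1.1 lists minor surgery next to 40 IU/kg dosing during pre-prophylaxis, without a port exception, and refers to Section 5.3.8.

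**The concern.** A protocol should give one instruction for one procedure. Here the section that site staff would open for minor surgery names port placement and gives one figure, while the dosing table gives another. The pointer meant to link the two leads to a symbol that is used twice.

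The protocol expects ports. They head its list of minor surgery examples, Section 8.2.4 deals with sealing them, and Section 8.4.3 deals with sampling through them. A site working from Section 8.7.1 alone and a site working from Table 5-1 alone would plan different preventive doses for the same procedure.

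The difference also matters for oversight. Section 8.7.1 requires the volume of the preventive dose to be recorded, and Section 18 requires deviations to be documented. The medication-error criterion for a medical event of special interest in Section 11.1 is judged against the intended dose. Each of these is harder to apply when the text gives two figures.

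**Working it through.** The point is a comparison of text, and the plan has no figure to reproduce. The instructions side by side:

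| Place in the protocol | Port placement | Port removal |
|---|---|---|
| Section 5.3.8, general sentence on minor surgery | 40 IU/kg, refers to Table 5-1 | 40 IU/kg, refers to Table 5-1 |
| Section 5.3.8, port entry in the list | sent to the asterisk in Table 5-1 | sent to the asterisk in Table 5-1 |
| Table 5-1, minor surgery cell | 80 IU/kg | not named; the general 40 IU/kg applies on its face |
| Table 5-1, asterisk footnote | ports not mentioned | ports not mentioned |
| Section 8.7.1 | 40 IU/kg recommended, refers to Table 5-1 | 40 IU/kg recommended, refers to Table 5-1 |

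**Placement.** Section 8.7.1 gives 40 IU/kg and Table 5-1 gives 80 IU/kg. The ratio is 80 / 40 = 2 and the difference is 80 − 40 = 40 IU/kg. This is more than a general rule that omits an exception, because the sentence just before the dose brings the port procedure in by name: "including placement or removal of central venous access port".

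**Removal.** Every figure that can be read as applying to removal is 40 IU/kg. No place states a second dose. The difficulty comes from Section 5.3.8, which attaches the asterisk to removal as well as implantation. A reader who follows it finds either an in-cell note on implantation only or a footnote on IWRS. Neither says whether the pointer was meant to give removal the implantation figure or was attached to it by oversight.

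**The asterisk.** It appears on the dosage header, inside the minor surgery cell and at the footnote. The footnote belongs naturally to the header, and the in-cell text follows its own asterisk directly. One symbol therefore marks two unrelated notes.

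**Effect on the analyses.** Section 5.3 counts an exposure day by calendar day of administration, regardless of the number of doses, and Section 5.3.8 includes treatment during surgery in that count. One preventive injection adds the same exposure day at either figure, so the exposure-day rule for the denominator of the inhibitor rate (Section 16.3) is unchanged. The consumption summaries in Section 16.4.2.4 concern prophylaxis and bleeding episodes; surgical doses are not listed there.

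**The case against.** The strongest reply is that the text works as a general rule with a specific exception. The dosing sentences in Sections 5.3.8 and 8.7.1 both send the reader to Table 5-1, and Section 8.5 ties administration to that table. The port exception sits in the very cell that the reader is sent to. Section 8.7.1 only recommends its figure and leaves preventive treatment to the investigator under local guidelines. Neither figure exceeds the maximum individual dose of 80 IU/kg in Section 9.1, which that section describes as relevant to surgery. The reused asterisk is a typographic matter, since only one of its uses mentions ports.

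Much of this stands. A careful reader who follows the cross-reference will see the 80 IU/kg figure. The documents do not show that sites did or would dose differently, and they give no number of expected port procedures. The reply still does not remove the conflict. Nothing in the protocol says that the table overrides the text, and the exception reading would be complete only if Section 8.7.1 were silent on ports. Discretion does not explain why the protocol's own figure changes between two places.

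A reader might also infer that removal is given two doses. The documents do not support that: Table 5-1 names implantation only, and no place states a second figure for removal.

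**Conclusion.** The inconsistency is real for port placement: 40 IU/kg in Section 8.7.1 against 80 IU/kg in Table 5-1, a twofold difference. For port removal there is an unclear cross-reference and no conflict between stated doses.

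This rests on reading placement in Section 8.7.1 and implantation in Section 5.3.8 and Table 5-1 as the same procedure, which their common classification as minor surgery supports. How often the question would arise is unknown. So is the figure that IWRS applies to a port procedure, because the table footnote says only that the system calculates the dose.

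Severity is the lowest. The reference to Table 5-1 and the investigator's discretion soften the conflict, and no endpoint analysis is affected. The reason to act is clarity of a dosing instruction in young children.

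**What to change.** The sponsor should reconcile Section 5.3.8, Table 5-1 and Section 8.7.1 so that port implantation and port removal each have one stated instruction, worded the same way wherever it appears. The port note in Table 5-1 should have its own symbol, separate from the footnote on IWRS, and the pointer in Section 5.3.8 should use that symbol and name only the procedures that the note covers. When this is done, the sponsor should also check that Section 8.1.1.1 and the IWRS dose calculation agree with the reconciled text. Which dose applies is for the sponsor to decide on clinical grounds, and no view is taken here.

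The cost is a few lines of wording in a protocol amendment. No change to visits, sample size or analysis is needed.

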8.7.2 Major surgery

Major surgery can be performed while participating in the present trial. For definition of major surgery, see Section [5.3.8](#). Novo Nordisk must be contacted in due time prior to surgery, to ensure sufficient supply of N9-GP.

N9-GP dosing prior to, during and after surgery should aim at FIX activity levels as defined and recommended in the WFH Guidelines for the management of haemophilia.⁸ The preoperative N9-GP dose should aim at FIX activity level of approximately 100% which is expected to be achieved with dose of 40 or 80 IU/kg of N9-GP. Trough and peak levels, and incremental recovery of the particular patient must be taken into consideration by the Investigator when deciding the dose.

During the post-operative phase, clinical haemostatic response combined with close FIX activity monitoring is recommended to determine appropriate intervals for postoperative dosing of 40 IU/kg N9-GP. The dose interval should be adjusted in order to reach postoperative FIX activity levels as recommended by the WFH Guidelines for the management of haemophilia.⁸

It is the responsibility of the Investigator to determine when the patient must stop the weekly prophylaxis administrations of N9-GP prior to the surgery and when these should be resumed after the surgery. If the patient has not resumed weekly prophylaxis within 6 days from the day of surgery the reason must be documented. The first weekly prophylaxis dose after surgery should be omitted if it falls on the same day (\pm 1day) as the last postoperative dose. The following must be documented:

- Date and time the patient stops the weekly prophylaxis with 40 IU/kg N9-GP prior to the surgery
- Date and time the patient resumes the weekly prophylaxis with 40 IU/kg N9-GP after the post-surgery period

Protocol
 Trial ID: NN7999-3895
 UTN: U1111-1135-9557
 EudraCT No.: 2012-004867-38

~~CONFIDENTIAL~~

| | | |
|----------|------------------|---------------------|
| Date: | 05 November 2019 | Novo Nordisk |
| Version: | 8.0 | |
| Status: | Final | |
| Page: | 68 of 119 | |

During this period, all bleeding episodes and any haemostatic treatment administered must be recorded in the eCRF when the patient is at the site and in the eDiary when the patient is at home, refer to Section [12.3](#).

Perioperative procedures, assessments and blood sampling will be performed at the Investigators discretion and documented in the patients' medical records.

- Type of surgery (e.g. arthroscopy), indication (e.g. prosthetic knee replacement) and location
- Elective or emergency surgery
- Duration of surgical procedure: The date and time of first incision (knife-to-skin) and skin closure (last stitch)
- Concomitant medication, including anaesthetics and haemostatic medication
- Clinical narrative incl. description of any complication, estimated blood loss, if any re-operations etc.
- Blood product transfusions, if any: Type, volume (mLs), Start date and time
- Other i.v. infusions, if any: Type (ex. saline, crystalloids/colloids), concentration and volume (mLs), Start date and time
- Haemoglobin measurements, if any
- Clinical evaluation of haemostatic response to be evaluated upon completion of the surgical procedure by the Surgeon, Anaesthesiologist and/or Investigator, based on experience as follows:
 - Excellent: Better than expected/predicted in this type of procedure
 - Good: As expected in this type of procedure
 - Moderate: Less than optimal for the type of procedure but haemostatic response maintained without change of treatment regimen
 - Poor: Bleeding due to inadequate therapeutic response with adequate dosing, change of regimen required

8.8 Training and reminders

8.8.1 Trial card dispensing

At V0 the patient's parent(s)/LAR(s) will receive a trial card stating that the patient is participating in a clinical trial. Telephone numbers and contact persons at the trial site will be listed.

8.8.2 Home treatment training

Home treatment training with administration of N9-GP can start after administrations of the first 3 EDs at trial site until V20 (see Section [8.1.12](#)), but may be postponed until the patient's parent(s)/LAR(s) are comfortable with the reconstitution and administration process.

A home treatment guide for the reconstitution will be available as handouts for the patient's parent(s)/LAR(s).

Protocol
 Trial ID: NN7999-3895
 UTN: U1111-1135-9557
 EudraCT No.: 2012-004867-38

~~CONFIDENTIAL~~

Date: 05 November 2019
 Version: 8.0
 Status: Final
 Page: 69 of 119

Novo Nordisk

Training in reconstitution and administration must be performed until parent(s)/LAR(s) feel comfortable in handling the treatment. The training must be documented in the medical records.

All patient's parent(s)/LAR(s) must be carefully instructed in recognising and dealing with signs and symptoms of an anaphylactic reaction. If the patient does not follow the planned dosing schedule, the investigator must retrain the patient's parent(s)/LAR(s).

8.8.3 Electronic diary (eDiary)

Pre-prophylaxis treatment, prophylaxis treatment and bleeding episodes should be recorded in eCRF for the first 20 EDs. When the first 20 EDs have been administered, the data will be captured either in eCRF and/or eDiary according to Section [12.3](#).

Parent(s)/LAR(s) should be trained in using the eDiary before or when they receive the eDiary. If needed the training must be repeated until the parent(s)/LAR(s) use the eDiary as intended.

It will be the responsibility of the investigator to assess the eDiary data throughout the conduct of the trial and to ensure entry compliance.

During the home treatment period the patient's parent(s)/LAR(s) should ensure that all prophylactic home treatment, bleeding episodes, treatment of bleeding episodes as well as haemostatic evaluation of the treatment of bleeding episodes are captured in the eDiary.

8.8.3.1 eDiary dispensing and collection

The eDiary will be dispensed to the patient's parent(s)/LAR(s) latest at the visit when home treatment is started.

For details regarding patient's diary, please refer to Section [12.3](#).

For patients completing the trial or in case of withdrawal, the eDiary will be collected at the EOT visit.

8.8.4 Contact between the investigator/medically qualified person and the patient

The investigator and/or medically qualified person must establish contact with the patient's parent(s)/LAR(s) at least every 12 weeks \pm 1 week, if site visits are more than 3 months apart, either by visits at the trial site or other contact e.g. telephone calls. All trial related contacts must be captured in eCRF.

The patient and patient's parent(s)/LAR(s) should be notified that they will be contacted according to the protocol.

The communication will focus on the well-being of the patient, including enquiry of all AEs, and any medical treatment (including treatment of bleeding episodes) since the last contact. The

Protocol
 Trial ID: NN7999-3895
 UTN: U1111-1135-9557
 EudraCT No.: 2012-004867-38

~~CONFIDENTIAL~~

| | | |
|----------|------------------|---------------------|
| Date: | 05 November 2019 | Novo Nordisk |
| Version: | 8.0 | |
| Status: | Final | |
| Page: | 70 of 119 | |

investigator/medically qualified person should not suggest specific AEs to patient's parent(s)/LAR(s), but should inquire e.g. "how is your child doing?", "has your child had any problems since the last contact?" and "have you remembered to enter all treatments in the eDiary?"

The expiration date of the drug and solvent that the patient has received should be checked by the site staff before the patient's next visit to determine if an extra visit is relevant and to inform the patient of which unused vials to return to the site. Expiry of injection kits should be discussed.

All attempts to contact the patient's parent(s)/LAR(s) must be documented in a source document. If a successful contact cannot be made after 3 documented attempts no further attempts are required. If the patient's parent(s)/LAR(s) have withdrawn consent, this must be documented.

At each contact the investigator will at a minimum capture/evaluate

- Assessment of bleeding episodes
- Adverse events
- Concomitant Medication
- eDiary compliance
- N9-GP administration compliance

